5.3 Lifestyle Considerations

5.3.1 Meals and Dietary Restrictions

5.3.1.1 Diet Restrictions

In Part 1, in each treatment period, and in Part 2 on Days 1 and 7, participants will fast from all food and drinks, except water, for at least 8 hours before the first dose of study intervention administration. Participants will fast from all food and drinks, except water, between first dose of study intervention administration and the first scheduled meal. Meals and snack(s) will be provided by the site staff at time points indicated in the study flowchart. Participants will fast from all food and drinks, except water, between meals and snacks. The overall composition of the meals will be at the discretion of the investigator however the meal content must be in compliance with the caffeine and the alcohol restrictions (see Section 5.3.2).

After the 24-hour postdose #2 procedures (for Part 1) or 24-hour postdose #1 procedures (for Part 2) have been completed, subsequent meals and snacks will be unrestricted in composition, and timing.

Approximately 240 mL of water will be provided during study intervention administration. Additional water may be provided in 50-mL increments if desired. Water will be restricted 1 hour before and 1 hour after study intervention administration.

Participants will also fast before laboratory safety evaluations in Part 1 Day 1 (Period 1 only) and in [REDACTED] Fasting requirements for laboratory safety evaluations are at least 8 hours prior to collection.

Although there will be no diet composition and timing restrictions while the participants are taking the study intervention at home on Day 2 to Day 6, the meal content must be in compliance with the caffeine and the alcohol restrictions (see Section 5.3.2).

Instructions on whether to take MK-6552 with or without food and/or drink may be modified during the study based on newly available data.

5.3.1.2 Fruit Juice Restrictions

Participants will refrain from the consumption of grapefruit juice, grapefruits, and grapefruit products beginning approximately 2 weeks before administration of the initial dose of study intervention, throughout the study including the washout interval between treatment periods and Parts 1 and 2 and until the poststudy visit.

Participants also will refrain from the consumption of all fruit juices 24 hours before and after study intervention administration in each treatment periods (Part 1) and on Days 1 and 7 (Part 2). On all other days during the study, consumption of fruits and fruit juices (except for grapefruit, grapefruit juices, and grapefruit products) is allowed.

5.3.2 Caffeine, Alcohol, and Tobacco Restrictions

5.3.2.1 Caffeine Restrictions

Participants are advised to refrain from consumption of caffeinated beverages or xanthine-containing products from 12 hours prior to the Screening Visit. A recheck may be needed if participants did not refrain from consuming caffeinated beverages or xanthine-containing products 12 hours prior to the Screening Visit.

Participants will refrain from consumption of caffeinated beverages or xanthine-containing products from:

- 12 hours before and after study intervention administration in each treatment period of Part 1 and on Days 1 and 7 of Part 2
- 12 hours before poststudy visit.

At all other times, caffeinated beverages or xanthine-containing products will be limited to no more than 3 units per day (1 unit = 120 mg of caffeine).

A list of common caffeine-containing products and their caffeine content is provided in Appendix 11.

5.3.2.2 Alcohol Restrictions

Participants are advised to refrain from consumption of alcohol 24 hours prior to the screening visit. A recheck may be needed if participants did not refrain from consuming alcohol 24 hours prior to the Screening Visit.

Participants will refrain from consumption of alcohol from:

- The EDS SOC washout period through Part 1 and Part 2 and until reinitiation of EDS SOC after completion of all study procedures in the last treatment period of Part 2 or until return to baseline at the discretion of the investigator.
- 24 hours before poststudy visit.

At all other times, alcohol consumption is limited to no more than approximately 2 alcoholic beverages or equivalent servings (1 serving is approximately equivalent to: beer <354 mL/12 ounces>, wine <118 mL/4 ounces>, or distilled spirits <29.5 mL/1 ounce>) per day.

5.3.2.3 Tobacco Restrictions

Participants will follow the smoking restrictions (and if applicable, the use of nicotine/nicotine-containing products) defined by the CRU.

During the study, if the participant is a smoker, they will limit the number of cigarettes (including ecigarettes/vaping) to 10 per day.

5.3.3 Activity Restrictions

Parts 1 and 2

Participants will avoid unaccustomed strenuous physical activity (ie, weightlifting, running, bicycling, etc) from the prestudy (screening) visit until administration of the initial dose of study intervention, throughout the study (including washout intervals between treatment periods and study parts), and until the poststudy visit.

Participants will avoid activities requiring high degree of attention such as driving a car from EDS SOC Washout Period until reinitiation of EDS SOC after completion of all study procedures in Part 2, Period 2.

Participants not on EDS SOC will also avoid activities requiring high degree of attention such as driving a car from participant randomization in Part 1 Period 1 Day 1 until completion of all study procedures in Part 2, Period 2.

Participant transportation needs will be covered by the Sponsor from the time driving restriction is in effect (EDS SOC Washout Period or randomization in Part 1 Period 1 Day 1) until completion of all study procedures in study Part 2, Period 2. Transportation options covered may include public transportation, family member, taxi, Uber, Lyft share rides, etc.

Part 2

Participants will avoid vigorous physical activity (ie, strength training, running, hiking or biking uphill, etc.) up to 4hours after study medication administration from Day 1, Period 1 until reinitiation of EDS SOC after completion of all study procedures in Period 2.

5.3.4 Bedtime

Throughout the study, participants should go to bed at their usual bedtime. To ensure at least 6 hours of sleep per night, starting in the first treatment period of Part 1 and throughout the study until reinitiation of EDS SOC treatment (after completion of all study procedures in Part 2 Period 2), participants will avoid going to bed pass midnight time.

5.3.5 Other

Participants will NOT engage in the following activities from the EDS SOC washout period, throughout the study (including washout intervals between treatment periods and study parts) and until reinitiation of EDS SOC treatment after completion of all study procedures in Part 2, Period 2).

- nighttime shift work
- travel across >3 time zones

5.4 Screen Failures

Screen failures are defined as participants who consent to participate in the clinical study but are not subsequently randomized in the study. A minimal set of screen failure information may be included, as outlined in the eCRF entry guidelines. Minimal information may include demography, screen failure details, eligibility criteria, and any AEs or SAEs meeting reporting requirements.

Participants may be rescreened as appropriate per Section 8.11.1.

5.5 Participant Replacement Strategy

If a participant discontinues from study intervention or withdraws from the study a replacement participant may be enrolled if deemed appropriate by the investigator and Sponsor. The replacement participant will generally receive the same intervention or intervention sequence (as appropriate) as the participant being replaced. The replacement participant will be assigned a unique treatment/randomization number.

6 STUDY INTERVENTION

Study intervention is defined as any investigational intervention(s), marketed product(s), placebo, or medical device(s) intended to be administered to a study participant according to the study protocol.

Clinical supplies study intervention(s) provided by the Sponsor will be packaged to support enrollment and replacement participants as required. When a replacement participant is required, the Sponsor or designee needs to be contacted before dosing the replacement participant. Clinical supplies will be affixed with a clinical label in accordance with regulatory requirements.

6.1 Study Intervention(s) Administered

The study intervention(s) to be used in this study are outlined in [Table 4](#).

Country-specific requirements are noted in Appendix 7.

Table 4 Study Interventions

CCI

CCI

EEA=European Economic Area; IMP=investigational medicinal product; NIMP/AxMP=noninvestigational/auxiliary medicinal product; CCI

The classification of IMP and NIMP/AxMP in this table is based on guidance issued by the European Commission and applies to countries in the EEA. Country differences with respect to the definition/classification of IMP and NIMP/AxMP may exist. In these circumstances, local legislation is followed.

All supplies indicated in [Table 4](#) will be provided per the “Sourcing” column depending on local country operational requirements. If local sourcing, every attempt should be made to source these supplies from a single lot/batch number where possible (eg, not applicable in the case where multiple lots or batches may be required due to the length of the study, etc).

Refer to Section 8.1.8 for details regarding administration of the study intervention.

6.2 Preparation/Handling/Storage/Accountability

6.2.1 Dose Preparation

Specific calculations or evaluations required to be performed to administer the proper dose to each participant are outlined in a separate document provided by the Sponsor. The rationale for selection of doses to be used in this study is in Section 4.3.

6.2.2 Handling, Storage, and Accountability

The investigator or designee must confirm appropriate temperature conditions have been maintained during transit for all study intervention received, and any discrepancies are reported and resolved before use of the study intervention.

Only participants enrolled in the study may receive study intervention, and only authorized site staff may supply or administer study intervention. All study interventions must be stored in a secure, environmentally controlled, and monitored (manual or automated) area in accordance with the labeled storage conditions with access limited to the investigator and authorized site staff.

The investigator, institution, or the head of the medical institution (where applicable) is responsible for study intervention accountability, reconciliation, and record maintenance (ie, receipt, reconciliation, and final disposition records).

For all study sites, the local country Sponsor personnel or designee will provide appropriate documentation that must be completed for drug accountability and return, or local discard and destruction if appropriate. Where local discard and destruction is appropriate, the investigator is responsible for ensuring that a local discard/destruction procedure is documented.

The study site is responsible for recording the lot number, manufacturer, and expiry date for any locally purchased product (if applicable) as per local guidelines unless otherwise instructed by the Sponsor.

The investigator shall take responsibility for and shall take all steps to maintain appropriate records and ensure appropriate supply, storage, handling, distribution, and usage of study interventions in accordance with the protocol and any applicable laws and regulations.

6.3 Measures to Minimize Bias: Randomization and Blinding

[figure not shown]
6.3.1 Intervention Assignment

Participants will be assigned randomly according to a computer-generated allocation schedule.

A sample allocation table is provided below in [Table 5](#).

Table 5 Allocation of Participants to Treatment

CCI

6.3.2 Stratification

No stratification based on age, sex, or other characteristics will be used in this study.

6.3.3 Blinding

Part 1 of this study is conducted as open label; therefore, the Sponsor, investigator, and participant will know the intervention administered.

In Part 2 of this study, a double-blinding technique will be used. MK-6552 and placebo will be prepared and/or dispensed in a blinded fashion by an unblinded pharmacist or qualified study-site personnel. The participant, the investigator, and Sponsor personnel or delegate(s) who are involved in the study intervention administration or clinical evaluation of the participants are unaware of the intervention assignments.

See Section 8.1.10 for the description of unblinding if a medical emergency occurs during the study.

6.4 Study Intervention Compliance

Interruptions from the protocol-specified treatment plan require consultation between the investigator and the Sponsor and written documentation of the collaborative decision on participant management.

When the individual dose for a participant is prepared from a bulk supply, the preparation of the dose will be confirmed by a second unblinded member of the study-site staff.

In Part 1 when participants are dosed at the site, they will receive study intervention directly from the investigator or designee, under medical supervision. The date and time of each dose administered in the clinic will be recorded in the source documents and recorded in the CRF. The dose of study intervention and study participant ID will be confirmed at the time of dosing by a member of the study-site staff other than the person administering the study intervention. Study-site personnel will examine each participant's mouth to ensure that the study intervention was ingested.

In Part 2 (Day 2 [afternoon dose only] and Days 3 to 6) when participants self-administer the study intervention at home, daily phone calls will be made to check study intervention administration compliance. Compliance with study intervention will also be assessed at the next on-site visit by direct questioning and site review of the completed study intervention dosing diary as captured by the participant. Compliance will also be assessed by counting returned capsules during the next on-site visit and documented in the source documents and CRF. Deviation(s) from the prescribed dosage regimen should be recorded in the CRF.

A record of the number of MK-6552/placebo capsules dispensed to and taken by each participant must be maintained and reconciled with study intervention and compliance records. Intervention start and stop dates, including dates for intervention delays and/or dose reductions will also be recorded in the CRF.

When participants are dosed at the site CCI, study intervention administration will be witnessed by the CRU staff. The staff will witness the participant record the dosing in the study medication diary.

6.5 Concomitant Therapy

If a participant does not discontinue all prior medications within 14 days or 5 half-lives of the first dose of study intervention, they may be included in the study if the investigator can rationalize that the specific use of a prior medication is not clinically relevant within the context of the study.

Concurrent use of any prescription or nonprescription medication, or concurrent vaccination, during time periods specified by this protocol for that medication must first be discussed between the investigator and Sponsor before administration, unless appropriate medical care necessitates that therapy or vaccination should begin before the investigator and Sponsor can consult. The participant will be allowed to continue in the study if both the Sponsor and the investigator agree.

COVID-19 and flu vaccines may be administered. Study intervention must be given at least 72 hours following or at least 48 hours prior to any COVID-19 vaccination.

Investigational COVID-19 (ie, those not licensed or approved for Emergency Use) are not allowed.

Paracetamol/acetaminophen may be used for minor ailments without prior consultation with the Sponsor.

In addition, the following concomitant medications are permitted:

Medications for treatment of cataplexy may be continued for the duration of the trial include selective serotonin reuptake inhibitors (SSRIs) and/or serotonin noradrenaline reuptake inhibitors (SNRIs).

Systemic contraceptives and hormone replacement therapy are permitted for POCBP participants.

6.5.1 Rescue Medications and Supportive Care

No rescue or supportive medications are specified for use in this study.

CRUs will be staffed with medically trained personnel with appropriate access to full-service acute care hospitals to facilitate rapid institution of medical intervention.

6.6 Dose Modification (Escalation)

Dose escalation decisions are applicable only to Part 1.

All dose-escalation decisions will be made jointly by the investigator and the Sponsor. Members of the Sponsor safety review team will include: the trial clinical director, trial clinical scientist(s), senior level clinical director and trial biostatistician. Additional Sponsor attendees may include a clinical research associate and a pharmacologist. The Sponsor safety review team will obtain input from the investigator regarding their evaluation of safety and tolerability from the previous dosing period and their recommendation to dose escalate in the next period.

Each dose-escalation decision will occur on an individual basis as the study enrollment of participants will be progressive and on-going throughout the study.

Dose-escalation decisions will be based on key safety variables, including VS, 12-lead ECG, laboratory safety tests, PE, NE, and AEs/SAEs from the previous dose levels up to at least 24 hours postdose #2. Additionally, individual stopping rules (Section 7.1.1) will be reviewed to confirm none of the rules are met. Pharmacokinetic data may be included in the dose-escalation decisions (Section 2.1 and Section 2.2).

If, as judged by the Sponsor and investigator, the safety and tolerability data do not justify dose escalation, the dose will not be increased as planned. Instead, individual participants may:

Receive the same dose level to further explore safety and tolerability at that level,

Receive a lower dose of the study intervention (with or without food),

Dosing in Part 1 may be stopped and participants may proceed to Part 2 at a dose up to the maximum safe and well tolerated dose reached in Part 1.

Participant discontinuation criteria are outlined in Section 7.

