Scheduled Day	Screening/Rescreening ^b	EDS SOC Washout Before Randomization (Remote Visit Through Phone Call)	D1											D2	Screening procedures to be completed within approximately 28 days ± 7 days from randomization	
CCI			CCI													
															CCI	
Serum (hCG; POCBP only)	X															Sec. 8.3.6, Appendix 2
Urine Pregnancy Test (POCBP only)			X													Sec. 5.1, 8.3.7 Urine pregnancy test to be completed in each treatment period
Serum FSH - (POCBP only)	X															Appendices 2 and 5
HIV, hepatitis B and C screen (per site SOP)	X															Sec. 5.2, Appendix 2
Drug screen (per site SOP)	X		X													Appendix 2 Screening drug screen is mandatory, any additional drug screens are conducted per site SOP. Alcohol test will be conducted using a breathalyzer. To be collected in Period 1 only Predose drug screen and alcohol test may be collected upon admission within 24 hours of dosing.

Part 1/All Panels/All Periods/Dose 1 and Dose 2 ^a																
Study Period:	Screening		Intervention													Notes:
Scheduled Day	Screening/Rescreening ^b	EDS SOC Washout Before Randomization (Remote Visit Through Phone Call)	D1												D2	Screening procedures to be completed within approximately 28 days ± 7 days from randomization
CCI			CCI													
Hematology, Chemistry, Urinalysis	X		X													Sec. 8.3.6, Appendix 2 In Period 1 only, blood for safety laboratory tests will be collected as follow: Dose 1: Predose
Safety Phone Calls		X														Sec. 8.3.10.1, 8.1.5.1 Washout period may vary based on the EDS SOC
AE/SAE review	X	X	X	X	X	X	X	X	X	X	X	X	X	X	X	Sec. 8.4, Appendix 3
Pharmacokinetics																
Blood for Plasma MK-6552 and or Metabolites Assay			X		X	X	X	X	X	X	X	X	X	X	X	Sec. 8.6.1, 8.11.5 In each treatment period, PK blood collection will be as follow: CCI

Part 1/All Panels/All Periods/Dose 1 and Dose 2 ^a																
Study Period:	Screening		Intervention													Notes:
Scheduled Day	Screening/Rescreening ^b	EDS SOC Washout Before Randomization (Remote Visit Through Phone Call)	D1											D2	Screening procedures to be completed within approximately 28 days ± 7 days from randomization	
CCI			CCI													
Pharmacodynamics																
PSG	X															Sec. 8.7.1
CCI	X		X				X					X	X			Sec. 8.7.3 In each treatment period completed at: CCI
CCI			X											X		Sec. 8.7.4 CCI

Part 1/All Panels/All Periods/Dose 1 and Dose 2 ^a																

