1.3.2 Part 2 Panel A

Part 2/Panel A/All Periods/Dose 1 and Dose 2 ^a														
													Poststudy	Notes:
CCI					CCI						CCI			
CCI	CCI													
Administrative/Study Procedures														
Prior/Concomitant Medication Review	X	X	X	X	X	X	X	X	X	X	X	X	X	Sec. 5.2, 6.5, 8.1.5
Study Intervention (MK-6552 or Placebo) Administration		X								X	X	X		Sec 8.1.8.1 CCI administration should be taken around the same time every day.

Part 2/Panel A/All Periods/Dose 1 and Dose 2 ^a													
												Poststudy	Notes:
CCI													
Study Medication Diary Dispensing/Review		X									X	X	Sec. 6.4, 8.1.8 In each treatment period, Study Medication Diary will be dispensed to participants on Day -1. CCI
Domiciling	X	X	X	X	X	X	X	X	X	X	X		Sec 8.1.11 CCI day and remain in the unit up to 24 hours postdose #1.

MK-6552-004-05 FINAL PROTOCOL
08XGHY

Part 2/Panel A/All Periods/Dose 1 and Dose 2 ^a													
												Poststudy	Notes:
CCI [REDACTED]	[REDACTED]												
[REDACTED]	[REDACTED]												
Safety Procedures													
Full physical examination	X										X	X	Sec 8.3.1 Not applicable for predose #2 CCI [REDACTED] [REDACTED]
General neurological examination	X											X	Sec. 8.3.2, Appendix 10 (Sec 10.10.1) CCI [REDACTED] [REDACTED] [REDACTED]

Part 2/Panel A/All Periods/Dose 1 and Dose 2 ^a													
												Poststudy	Notes:
CCI													
Targeted neurological examination					X			X			X		Sec. 8.3.2, Appendix 10 (Sec 10.10.2) In each treatment period targeted NE will be conducted as follows: CCI
VS (HR, BP)	X				X			X				X	Sec 8.3.4.1 In each treatment period predose (baseline) will be in triplicate measurements. Postdose time-points will be in single measurement. Dose1: Predose, 2-, 6-hours postdose 1 Dose 2: 2 hour postdose 2
12-lead ECG	X						X					X	Sec 8.3.5, Appendix 8 In each treatment period ECG at Predose (baseline) will be in triplicate measurements. Postdose ECG time-points will be in single measurement. CCI

Part 2/Panel A/All Periods/Dose 1 and Dose 2 ^a														
													Poststudy	Notes:
CCI														
Urine Pregnancy Test (POCBP only)	X												X	Sec. 5.1, 8.3.7 In each treatment period urine pregnancy test to be completed on Day 1 only
Hematology, Chemistry, Urinalysis	X										X		X	Sec. 8.3.6, Appendix 2 In each treatment period blood for safety laboratory tests will be collected as follow: CCI
AE/SAE review	X	X	X	X	X	X	X	X	X	X	X	X	X	Sec 8.4, Appendix 3

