8.11.5 Critical Procedures Based on Study Objectives: Timing of Procedure

Part 1

The blood sample for MK-6552 is the critical procedure.

At any postdose time point, the blood sample for MK-6552 needs to be collected as close to the exact time point as possible.

CCI

All other procedures should be completed as close to the prescribed/scheduled time as possible. Study procedures can be performed before or after the prescribed/scheduled time.

The order of priority can be changed during the study with joint agreement of the investigator and the Sponsor Clinical Director.

Any nonscheduled procedures required for urgent evaluation of safety concerns take precedence over all routine scheduled procedures.

The following variance in procedure collection times will be permitted.

- PK Collection as outlined in [Table 7](#).

Table 7 Pharmacokinetic Blood Collection Windows

PK Collection	PK Collection Window
Predose	Up to -1h
0 to <1 h	±5 min
1 to <18 h	±15 min
18 to ≤24 h	±1 h

Study Intervention Administration

Study intervention administration: within 30 minutes of the theoretical administration time

Predose and Postdose Procedures

CCI

Postdose VS evaluations:

- Prior to 1 hour postdose may be obtained within 5 minutes of the scheduled sampling time
- Prior to 24 hours postdose may be obtained within 15 minutes of the scheduled sampling time

The PK sampling scheme currently outlined in the protocol may be modified during the study based on newly available PK data (eg, to obtain data closer to the time of peak plasma concentrations). If indicated, these collected samples may also be assayed in an exploratory manner for metabolites and/or additional pharmacodynamic markers.

Up to additional 50 mL of blood may be drawn for safety and/or PK analyses. The total blood volume withdrawn from any single participant will not exceed the maximum allowable volume during their participation in the entire study (refer to the Central Laboratory Services Manual for approximate total blood volume to be drawn for each participant).

CCI [REDACTED]
[REDACTED]. Additional laboratory safety tests may be added to blood samples previously drawn to obtain additional safety information. These changes will not increase the number of study procedures for a given participant during their participation in the entire study.

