10.2 Appendix 2: Clinical Laboratory Tests

The tests detailed in [Table 8](#) will be performed by the central laboratory.

Local laboratory results are only required in the event that the central laboratory results are not available in time for either study intervention administration and/or response evaluation. If a local sample is required, it is important that the sample for central analysis is obtained at the same time. Additionally, if the local laboratory results are used to make either a study intervention decision or response evaluation, the results must be entered into the CRF.

Protocol-specific requirements for inclusion or exclusion of participants are detailed in Section 5 of the protocol.

Additional tests may be performed at any time during the study as determined necessary by the investigator or required by local regulations.

Table 8 Protocol-required Safety Laboratory Assessments

Laboratory Assessments	Parameters			
Hematology	Platelet Count	RBC Indices: MCV MCH Reticulocytes		WBC count with Differential: Neutrophils Lymphocytes Monocytes Eosinophils Basophils
	RBC Count			
	Hemoglobin			
	Hematocrit			
Chemistry	BUN	Potassium	AST/SGOT	Total bilirubin (and direct bilirubin, if total bilirubin is above the ULN)
	Albumin	Bicarbonate	Chloride	Phosphorous
	Creatinine	Sodium	ALT/SGPT	Total Protein
	Glucose (fasted) ^a	Calcium	Alkaline phosphatase	
Routine Urinalysis	
 Specific gravity pH, glucose, protein, blood, ketones, nitrite, leukocyte esterase by dipstick Microscopic examination (if blood or protein is abnormal) 			
Pregnancy Testing	
 Highly sensitive serum (Screening Visit) OR urine (predose in each treatment period) hCG pregnancy test (as needed for POCBP) 			

Laboratory Assessments	Parameters
Other Screening Tests	
 • FSH (as needed in PONCBP only) • Breath alcohol test • Urine drug screen (to include at minimum: amphetamines, barbiturates, cocaine, opiates, cannabinoids, and benzodiazepines) • Serology (HIV antibody, HBsAg, and hepatitis C virus antibody) • Genotyping for HLA-DQB1*06:02 allele • All study-required laboratory assessments will be performed by a central laboratory

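### Part 1 escalation is to be based on laboratory safety tests through 24 h after the second dose, but no safety laboratory draw is scheduled after any Part 1 dose

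*Combined protocol and SAP*

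**What the plan says.** Section 6.6 limits escalation decisions to Part 1 and names the data behind them: vital signs, 12-lead ECG, and "laboratory safety tests, PE, NE, and AEs/SAEs from the previous dose levels up to at least 24 hours postdose #2". It adds that "Each dose-escalation decision will occur on an individual basis", with the investigator's evaluation of the previous dosing period as an input. If escalation is not justified, one option is that "Dosing in Part 1 may be stopped and participants may proceed to Part 2" at a dose no higher than the highest one tolerated.

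The Part 1 Schedule of Activities (Section 1.3.1) covers all panels and all periods. Its hematology, chemistry and urinalysis row is marked at screening and in the Day 1 predose column only, and the note reads: "In Period 1 only, blood for safety laboratory tests will be collected as follow: Dose 1: Predose". Section 5.3.1.1 ties the Part 1 laboratory fast to the same single occasion: "Participants will also fast before laboratory safety evaluations in Part 1 Day 1 (Period 1 only").

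Routine laboratory draws return in Part 2. For Panel A the schedule states: "In each treatment period blood for safety laboratory tests will be collected as follow", and Panel B has the same note. The draw times themselves are redacted.

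**The concern.** The escalation rule names a safety input that the schedule never generates. The team would have to escalate without it or order tests ad hoc.

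The study is the first to give MK-6552 to people with narcolepsy type 1 (Section 2.1). Escalation is decided participant by participant, and there is no data monitoring committee (Section 10.1.4). Part 1 omits placebo so that as much safety data as possible is gathered on active drug (Section 4.2.2). Laboratory tests are among the primary safety endpoints (Section 9.3.1) and are to be summarized as change from baseline where clinically appropriate (Section 9.5.1), yet Part 1 has no scheduled post-dose value for such a summary. Potential drug-induced liver injury is defined by laboratory values (Section 8.4.7), so before Part 2 it could be found only through unscheduled or add-on testing.

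**Working it through.** This is mainly a comparison of sections, with simple counts. The plan gives no figure of its own to reproduce.

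**Inputs**
- Part 1 has four periods per panel (Section 1.2, Table 1).
- There are two doses per period, about 6 h apart (Section 1.3.1, dosing row).
- Dosing is at least 4 days apart between Part 1 periods, and between Part 1 and Part 2 (Section 1.2, Table 1 footnotes d and g). The summary of changes gives about 7 days as the sites' usual spacing.
- Participants stay in the unit until at least 24 h after dose 2 (Section 1.3.1, domiciling row).

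**What escalation needs and what Part 1 schedules after dosing**

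| Input named in Section 6.6 | Marked on Day 2 of each Part 1 period? |
|---|---|
| Vital signs | Yes |
| ECG | Yes |
| Physical examination | Yes |
| Neurological examination (targeted) | Yes |
| Adverse events | Yes |
| Laboratory safety tests | No |

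The laboratory row and its note are unredacted, and the note ends at the Period 1 predose draw. The blank is therefore not produced by redaction.

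**Counts for a participant given all four periods**
- Doses: 4 × 2 = 8.
- Escalation decisions: 4 − 1 = 3.
- Scheduled post-dose laboratory sets before those decisions: 0.

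**Gap from the Period 1 predose draw to the first Part 2 draw**

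After k periods at minimum spacing the gap is 4k days if spacing runs from dose 1. It is 4k days + 6k h if spacing runs from dose 2 to the next dose 1. The first Part 2 draw is assumed to be Day 1 predose.

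| k | From dose 1 | From dose 2 |
|---|---|---|
| 1 | 4 days | 4 days 6 h |
| 2 | 8 days | 8 days 12 h |
| 3 | 12 days | 12 days 18 h |
| 4 | 16 days | 17 days |

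At 7-day spacing, k = 4 gives 4 × 7 = 28 days.

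**Is there time to use a result drawn 24 h after dose 2?**

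The draw falls 6 + 24 = 30 h after dose 1.
- 4-day spacing (96 h): 96 − 30 = 66 h remain if spacing runs from dose 1, and 96 − 24 = 72 h if it runs from dose 2.
- 7-day spacing (168 h): 168 − 30 = 138 h and 168 − 24 = 144 h.

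**The case against.** The schedule mismatch is not in dispute. The case on the other side is about how much it matters.

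*Post-dose tests are already permitted.* Appendix 2 says: "Additional tests may be performed at any time during the study as determined necessary by the investigator". The permitted-modifications text at the end of Section 8.11 says: "Additional laboratory safety tests may be added to blood samples previously drawn to obtain additional safety information", allows up to 50 mL of extra blood for safety or PK, and lets alterations be documented by a letter to the study file. This is true and softens the practical effect. None of it makes a laboratory result a condition of escalation. The same text also says that the changes it describes will not add study procedures for a participant, which fits poorly with a routine extra draw.

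*Section 6.6 can be read loosely.* It refers to previous dose levels in the plural and enrollment is progressive, so the team might review whatever laboratory data exist, including earlier participants' Part 2 results. Pooling Part 1 data adds nothing, because no participant has a scheduled post-dose Part 1 set. Part 2 results come from a blinded comparison with placebo in other people. Section 9.6 allows unblinded aggregate summaries, but these do not replace the participant's own results.

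*Relevant text may be redacted.* Section 7.1.1 and stopping rules 4 to 6 in Section 6.6.1 could contain laboratory triggers. If so, Part 1 would still have no scheduled post-dose draw to set them off.

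*The placement may be deliberate and the risk modest.* Part 1 is single-day dosing, and the amendment added a Day 4 draw for Panel B in Part 2, where dosing runs over several days. PN002 completed multiple dosing in healthy participants up to 7.0 mg twice daily, with data still blinded (Section 2.2.3). The summary of changes gives a Panel B range of 1 to 4 mg, and Section 4.3 already cites Part 1 PK from 4 participants with narcolepsy. This stands as a reason not to call the matter critical. It does not reconcile the rule with the schedule.

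**Conclusion.** The concern holds. Section 6.6 and the Part 1 schedule cannot both be followed as written: with four periods, 3 escalation decisions and 8 doses pass with no scheduled post-dose laboratory result. The sponsor should correct this, but it is not a failure of the whole escalation review, since the other named inputs are scheduled through Day 2.

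The counts assume that all four periods are given. The 4-to-16-day gaps are minimums and assume that the first Part 2 draw is Day 1 predose, because the Part 2 draw times are redacted. Measuring spacing from dose 2 adds about 6 h per period and does not change the conclusion.

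**What to change.** Add hematology and chemistry at 24 h after dose 2 to the Section 1.3.1 schedule for every Part 1 period, taken with the Day 2 PK blood. Allow a non-fasting draw if needed, as footnote a to Table 8 already does for Panel B on Day 4. Where central results would arrive after the next dose, use a local result with a central sample taken at the same time, as Appendix 2 provides. The sets from Periods 1 to 3 then inform the 3 escalation decisions, and the Period 4 set informs the Part 2 dose.

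The cost is one schedule row changed by amendment and up to 4 extra sets per participant, or 3 if limited to the escalation decisions. The documents do not give the volume per set. At an assumed 5 to 10 mL, four sets take 4 × 5 = 20 mL to 4 × 10 = 40 mL. That is no more than the 50 mL of additional blood the protocol already contemplates, and should be checked against the maximum in the laboratory manual. Turnaround must fit about 66 to 72 h at minimum spacing. The 4-day interval already provides for data entry (Section 8.11.2).

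Deleting laboratory tests from the Section 6.6 list would also make the text consistent if the sponsor judges the draws unnecessary. It is the weaker choice, because it would also drop any unscheduled abnormal result from the named inputs.
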